- Known or suspected allergy to Dapagliflozin, excipients, or related products
- Pregnant, breast-feeding or the intention of becoming pregnant
- Females of childbearing potential who are not using adequate contraceptive methods

Withdrawal Criteria

Study subject may withdraw at will at any time.

Repeated eGFR <60 mL/min/1.73 m² and hypoglycaemic (< 70 mg/dl) episodes will mandate discontinuation of the patient from the study.

VISIT PROCEDURES

Once patient eligibility and written consent are obtained, the participant is then scheduled for the baseline (t0) clinic visit through the University of Miami UChart (Epic) electronic system. The visits will be coordinated by the research coordinator. Each patient will undergo a baseline echocardiographic study for the measurement of EAT and LVM. Each patient will also have a full physical examination, body weight, height, waist and hip circumference measured, a point of care of fasting glucose and haemoglobinA1c (HbA1c). Echocardiographic study will be performed on site by [name] and by an experienced cardiac imaging technician who will be trained to measure echocardiographic EAT by [name]. The same visit procedures will be repeated after 3 (t3) and 6 (t6) months.

DESCRIPTION OF STUDY SITE

UM Miller School of Medicine has been the site of several National Institutes of Health studies and many peer-reviewed, epidemiologic and health services research publication. The Division of EDM is fully equipped and trained to visit, follow up and manage patients with diabetes. UMMG-DRI is fully accredited and equipped to perform state-of-the-art diagnostic tests assisting in the diagnosis and management of diabetes. The Division is also equipped with a state-of-the-art echocardiographic unit, Siemens, Acuson, USA, for the measurement of the EAT. [name] pioneered the echocardiographic measurement of the epicardial fat and he is considered the leading expert in epicardial fat research

METHODOLOGY

Informed consent will be in place before any study related procedures will be conducted.

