Echocardiographic Epicardial Fat Thickness Echocardiographic studies will be performed onsite by [name] and a technician trained in echocardiography. Standard parasternal and apical views will be obtained in the left lateral decubitus position. All echocardiograms will be recorded on DVDs and subsequently digitized will be analyzed offline for epicardial fat thickness quantification according to the method firstly described and validated by [name] et al (9-10). Briefly, epicardial fat will be identified as the echo-free space between the outer wall of the myocardium and the visceral layer of pericardium. Epicardial fat thickness will be measured perpendicularly on the free wall of the right ventricle at end-systole in three cardiac cycles. Parasternal long- and short-axis views allow the most accurate measurement of epicardial adipose tissue on the right ventricle, with optimal cursor beam orientation in each view. Maximum epicardial fat thickness will be measured at the point on the free wall of the right ventricle along the midline of the ultrasound beam, perpendicular to the aortic annulus, used as anatomical landmark for this view. For the midventricular parasternal short-axis assessment, maximum epicardial fat thickness will be measured on the right ventricular free wall along the midline of the ultrasound beam, perpendicular to the interventricular septum at mid-chordal and tip of the papillary muscles level, as anatomic landmark. The average value of three cardiac cycles from each echocardiographic view will be considered.

Reliability of echocardiographic measurement of EAT

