Reliability of echocardiographic measurement of EAT will be assessed by the intra-class correlation coefficient. Inter- and intra-observer reproducibility will be evaluated by the intra-class correlation coefficient in all subjects. Echocardiograms will be read by [name] and an experienced cardiac imaging technician who will be blinded to the patients' study group. Previously published studies have shown that intra- and inter-observer reproducibility of epicardial fat measurement was excellent. Intra-class correlation coefficients varied from 0.90 to 0.98 and from 0.93 to 0.98, respectively indicating good reproducibility and reliability. Both readers will be blinded to the subjects' clinical data. Although its advantages overcome the disadvantages, echocardiography measurement may have some limitations. Echocardiographic EAT is a linear measurement at a single location and therefore may not reflect the variability of fat thickness or total epicardial fat volume

Echocardiographic LVM and LVH measurement

LV mass will be estimated by using the anatomically validated formula of Devereux, and then adjusted as LV mass/body surface area (BSA) and LV mass/height^{2.7} (h^{2.7}). Left ventricular hypertrophy (LVH) will be defined as LV mass/BSA >134 g/m² for men and >110 g/m² for women and as LV mass/h^{2.7} >51 g/m^{2.7} in both sexes. Relative wall thickness (RWT) will be calculated as 2 posterior wall (PW)/LV end – diastolic – diameter. Four LV geometric patterns (normal, concentric remodeling, concentric hypertrophy, and eccentric hypertrophy) will be determined using values of RWT and LV mass as follows: normal (no LVH and RWT < 0.44), concentric remodeling (no LVH and RWT > 0.44), concentric hypertrophy (LVH and RWT > 0.44), and eccentric hypertrophy (LVH and RWT < 0.44).

Physical Examination

All anthropometric measures will be obtained by the study nurse. Height (in cm) and weight (in kg) will be measured, and BMI will be automatically calculated as weight in kilograms divided by the square of height in meters (kg/m²). Waist circumference (in cm) will be measured as the minimum circumference between the lower rib margin and the iliac crest. Hip circumference (in cm) will be measured as the widest diameter over the greater trochanters). Blood pressure will be measured in the seated position, using an automated cuff and digital readout, and entered by the study nurse into the electronic database.

Blood Measurements

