We expect that Dapagliflozin will cause a significant decrease in EAT, but much smaller when compared to weight loss interventions such as a VLCD. EAT decrease has been shown to vary (between -12% and -32%) after different interventions. EAT reduction is anticipated to be between -15% and -25% after 3 months of treatment with Dapagliflozin. A hypothesis of at least 15% reduction in EAT is based on: a) the previously reported weight-loss caused by Dapagliflozin, b) previously-reported responsiveness (decrease) of EAT to pharmacological agents targeting the fat. A reduction of 15%, an absolute difference of 1.2 mm from baseline, will be considered not only statistically, but clinically significant of visceral fat reduction. It is worthwhile to note that a reduction of 0.4 and 1.4 mm in EAT after atorvastatin and bariatric surgery, respectively, was previously considered statistically and clinically significant. However, it is possible to expect a larger difference after 6 months of treatment

Given the reference value and the expected difference in EAT, the statistical power of the study (two-sided, $\alpha=0.05$) was calculated.

Outcome	Reference value \pm SD	Expected Difference	Detectable difference with 80% power $\alpha=0.05$	Detectable difference with >99% power $\alpha=0.05$
EAT (mm)	8 ± 3	-15-or -25%	-15% (absolute difference = 1.2)	-25% (absolute difference = 2)

A convenience sample of 50 individuals for each group will therefore provide the statistical power (80%) to detect an expected difference of -15% in the EAT before and after treatment with Dapagliflozin. Baseline SD of 3 is expected to lower to approximately 2 for the expected change. The expected change of SD will assure significant statistical power of the comparative test.

Study Hypothesis 1 Dapagliflozin causes a significant and rapid decrease in EAT. Comparative statistical analysis between F and M-group will be performed to tests this hypothesis. Continuous variables will be considered as age-adjusted and sex-adjusted means with their standard deviations (SDs). Two-tailed $p < 0.05$ indicates statistical significance. ANOVA model with adjustment for baseline will be used to calculate the changes (Δ) in EAT between baseline, 3 and 6 months in both F and M-group.

Study Hypothesis 2

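### Masking the echo readers to visit and scan date, with random reading order, is a cheap safeguard for the before-after EAT and LVM changes; the documents do not mention it

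*Combined protocol and SAP*

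**What the plan says.** Three parts of the combined protocol and SAP bear on this.

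- **Masking.** The Methodology subsection on reliability of the EAT measurement names two readers, the investigator and "an experienced cardiac imaging technician who will be blinded to the patients' study group". Grammatically the group-masking clause attaches to the technician and may not reach the investigator. The subsection adds: "Both readers will be blinded to the subjects' clinical data". Visit, scan date and reading order are not mentioned there or elsewhere.
- **Acquisition and reading.** The Methodology subsection on epicardial fat thickness says: "Echocardiographic studies will be performed onsite by [name] and a technician trained in echocardiography". These appear to be the same two people who later read the scans. It continues: "All echocardiograms will be recorded on DVDs and subsequently digitized will be analyzed offline for epicardial fat thickness quantification". Under Visit Procedures, after the baseline scan: "The same visit procedures will be repeated after 3 (t3) and 6 (t6) months".
- **Expectation and use.** Statistical Considerations says: "EAT reduction is anticipated to be between -15% and -25% after 3 months of treatment with Dapagliflozin". It treats "A reduction of 15%, an absolute difference of 1.2 mm from baseline" as clinically significant and words its power statement as before versus after dapagliflozin. Hypothesis 1 is nevertheless tested between the dapagliflozin group (F) and the metformin-plus-placebo group (M), with adjustment for baseline. Hypothesis 2 uses changes in LVM in both groups and regressions of change in LVM on change in EAT.

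On trial blinding, Study Design describes a double-blind, placebo-controlled study, whereas the Randomization paragraph calls it open.

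**The concern.** EAT is read by hand, as the maximum thickness of a layer expected to average about 8 mm. A reader who knows that a clip is a follow-up scan, and expects a fall, can place the calipers slightly tighter without intending to. Masking to arm does not prevent this, because the expectation attaches to the visit. The published intra-class correlations that the protocol cites do not settle it either: they measure agreement, and two readers with the same expectation can agree while both read low.

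At stake are the results that compare a patient with their own baseline: the within-arm changes in EAT and LVM, and the judgement that a 1.2 mm fall is clinically significant. The protocol notes that a 0.4 mm fall in EAT was previously regarded as clinically significant, so even a small reading shift matters on the plan's own scale. The ROC analysis, which predicts reduction in LVM, could also be affected, since a shift in LVM readings changes which patients count as reduced. The between-arm comparison is exposed only if readers also know or guess the arm.

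**Working it through.** **Inputs from Statistical Considerations.** 50 patients per arm; two-sided alpha 0.05; reference EAT 8 mm with SD 3 mm; SD of about 2 mm expected for the change; target difference 0.15 × 8 = 1.2 mm.

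**Assumed input.** The documents give no size for a reading shift b. I take b = 0.2 to 0.5 mm, which is 17% to 42% of 1.2 mm.

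**Step 1: the plan's own power figure.** One-sample before-after formula, n = 50, SD 3:

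- SE = 3/√50 = 0.424 mm.
- For 1.2 mm: Φ(1.2/0.424 − 1.96) = Φ(0.868) = 80.7% (79.2% with the t distribution).
- For 2 mm: 99.7% (t: 99.6%).

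This matches the stated 80% and >99%. A two-sample test with SD 2 and 45 per arm (10% dropout) also fits: 81.2% and 99.7%. With 50 per arm a two-sample test gives 51.6% at SD 3 and 85.1% at SD 2 for 1.2 mm. So the before-after reading of the power statement is supported by the numbers but not proved by them.

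**Step 2: within-arm test, no true change, shift b.** The test statistic is noncentral t with 49 df and noncentrality b/(SD/√50).

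| SD of change | SE (mm) | b = 0.2 mm | b = 0.5 mm |
|---|---|---|---|
| 2 mm | 0.283 | ncp 0.71, rejects 10.7% | ncp 1.77, rejects 41.0% |
| 3 mm | 0.424 | ncp 0.47, rejects 7.5% | ncp 1.18, rejects 21% |

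With b = 0 each rate is 5%. SD 2 is the plan's expectation for the change; SD 3 is the baseline value, used here as a cautious bound.

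**Step 3: F versus M with the same shift in both arms.** The difference is (change in F − b) − (change in M − b), so b drops out. A simulation of the baseline-adjusted comparison (4,000 trials per scenario, SD 3 at each visit, SD of change 2) gave an estimate of about 0 mm and type I error of 4.6% to 5.4% for common shifts of 0.4 to 1.2 mm.

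**Step 4: F versus M when the arm is known or guessed.** SE = 2 × √(2/50) = 0.4 mm, 98 df.

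- Shift on every F patient and no M patient: ncp 0.2/0.4 = 0.5 to 0.5/0.4 = 1.25, rejecting in about 8% to 24%.
- Shift on patients guessed to be on F, with accuracy a: the arm difference is (2a − 1) × b. At a = 60% it is 0.04 to 0.10 mm, rejecting in 5.1% to 5.7%. At a = 75% it is 0.10 to 0.25 mm, rejecting in 5.7% to 9.5%.

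**Step 5: EAT-LVM regression.** Subtracting one constant from every EAT change and another from every LVM change alters only the intercept. Slope and correlation are unchanged.

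**The case against.** The strongest reply is that the test named for Hypothesis 1 compares F with M and adjusts for baseline, and Step 3 shows that a common additive shift leaves it unbiased. That stands. A proportional under-reading at follow-up would not create a difference either: at 5% to 15% it would shrink a true 1.2 mm to between 1.14 and 1.02 mm.

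Several stronger readings are tempting, and the documents do not support them.

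- *That readers will know the visit.* The documents are silent; they do not say so. That the readers apparently acquire the scans makes it likely, not certain.
- *That every reported result is compromised.* The between-arm test is not, while arm masking holds.
- *That the shift manufactures an EAT-LVM association.* A constant shift cannot (Step 5). Only shifts that vary between patients and affect both measures could.
- *That drift accumulates over the whole study.* Each within-patient change spans at most six months, and randomised arms share any drift.
- *That 8% to 24% is the expected error of the primary test.* It requires perfect knowledge of arm; partial guessing gives much less (Step 4).
- *That LVM reading is plainly unmasked.* The masking sentences sit under the EAT heading but speak of echocardiograms generally, so their reach is unclear.

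It is also fair to say that coding clips does not mask image acquisition, such as view and beam orientation, and cannot remove recall of a scan.

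The reply is weaker on relying on arm masking. The group-masking clause clearly covers only the technician, and the protocol calls the trial both double-blind and open.

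**Conclusion.** This is a worthwhile, low-cost improvement of minor to moderate severity while arm masking holds. No masking to visit or scan date and no reading order is stated, and the expected direction of change is written into the protocol. The exposed results are the within-arm EAT and LVM changes and the before-after 1.2 mm criterion. For an assumed shift of 0.2 to 0.5 mm and no true EAT change, within-arm false-positive rates would be about 11% to 41% (SD 2 mm) or 7.5% to 21% (SD 3 mm). The size of the shift is an assumption throughout. The F-versus-M contrast is affected only through failure of arm masking, with about 8% to 24% as the worst case at SD 2 mm. The conflict over trial blinding means that failure cannot be dismissed. No sample size or power figure changes.

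**What to change.** In the Methodology subsections on EAT measurement and its reliability, state that both readers are masked to arm, patient identity, visit and scan date. State that each patient's digitised t0, t3 and t6 clips are stripped of identifiers and dates, coded, and read offline in random order after that patient's last visit, and that the code is released only once the readings are locked. Apply the same rule to LVM, and say so in the LVM subsection. Separately, reconcile the double-blind description under Study Design with the open description under Randomization.

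The cost is a sentence or two of protocol text and the coding of clips already due to be recorded, digitised and, for EAT, read offline. Readings wait until a patient's last visit; no eligibility or withdrawal criterion in the protocol uses EAT or LVM. Masking of acquisition is not achieved by this change and should be acknowledged as a remaining limitation.

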- a) Dapagliflozin causes a rapid and significant reduction of EAT in type 2 diabetic patients
- b) Dapagliflozin-induced EAT reduction would be associated with a significant reduction of LV mass, independent cardiovascular risk factor.

ENDPOINTS:

Primary Endpoint: EAT (Epicardial fat thickness) will be measured with echocardiography according to the method described and validated by [name] et al. Full description of the measurement is reported in the section "Methodology"

Secondary Endpoint: LVM (left Ventricular Mass) will be measured with echocardiography according to the standard formula, fully described in the section "Methodology"

SPECIFIC OBJECTIVES

Primary Objective:

- a) Does treatment with Dapagliflozin cause a significant decrease in EAT in subjects with type 2 diabetes?

Secondary Objective:

- b) Does treatment with Dapagliflozin cause a significant decrease in LVM, through the reduction of EAT, in subjects with type 2 diabetes?

[figure not shown]
STUDY DESIGN

This will be an interventional, double-blind, parallel group, placebo controlled study in 100 overweight/obese type 2 diabetic subjects who are taking Metformin as monotherapy.

Individuals will be randomized in two groups of 50 patients, to receive additional Farxiga (Dapagliflozin) (F-group) or to remain on Metformin (M-group) plus placebo orally once daily.

[figure not shown]
- F-group: Dapagliflozin will be administered at the starting dose of 5 mg once daily, then if no safety issues will occur, it will be titrated up to 10mg once daily after 2 weeks. Metformin (from 500 mg twice daily to a maximum of 1000 mg twice daily) regimen will be continued to achieve fasting glucose between 80 and 140 mg/dl.
- M-group will be treated with Metformin plus placebo orally once daily for the duration of the study. Metformin (from 500 mg twice daily to a maximum of 1000 mg twice daily) regimen will be continued to achieve fasting glucose between 80 and 140 mg/dl.

Both groups will receive lifestyle and diabetes education, as part of the standard care.

STUDY TIMETABLE

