Dapagliflozin reduces LVM through an effect on EAT. Based on our previous data (36) we know that LVM reduction is independently related to epicardial fat reduction. We hypothesize that LVM will reduce in the F-group and better than in the M-group. ANOVA test with 95% CI will be used to calculate the changes (Δ) in study parameters between baseline, 3 and 6 months in both F and M-group. Relations between Δ epicardial fat, Δ BMI, Δ waist circumference and Δ LVM will be calculated using simple linear regression analysis. Variables with a $p < 0.1$ value on univariate analysis will be entered in different multivariate analysis models to assess the independent determinants of Δ LVM, as dependent variables. Echocardiographic epicardial fat will be compared to BMI, waist circumference and to waist-hip ratio as independent predictor of Δ LVM. The optimum sensitivity and specificity of threshold values of EAT to predict reduction in LVM will be examined by receiver operating characteristics (ROC) analysis by plotting sensitivity vs. 100 – specificity.

DATA HANDLING AND RECORD KEEPING:

Data Collection: Each of the dedicated clinic exam rooms at the UMMG-DRI provides direct access to the clinical research study electronic data capture (EDC) eVelos system provided by the Clinical Research Informatics and Data Management Unit of the Center for Health Informatics and Bioinformatics at UM. The sponsor investigator and research coordinator will collect and manage the data.

ETHICS:

Informed Consent

Eligible and willing participant will be contacted by the research coordinator and consented. Previous to the signing of the informed consent, extensive oral and written information will be given to the subjects, including information about risks associated with Dapagliflozin treatment (in accordance with the updated Prescribing Information) before initiating any study related activity.

Confidentiality of data The sponsor investigator will explain that participant confidentiality will be maintained, data will only be identified by a number and that their consent forms with identification number will be kept locked in a filing cabinet.

Protections against Risk

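### The LVM comparison names no baseline covariate, although the EAT model does and baseline LVM is measured; one stated covariate set per endpoint would gain precision at no cost

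*Combined protocol and SAP*

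**What the plan says.** Three statements about adjustment stand in the Statistical Considerations of the combined protocol and SAP.

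- Study Hypothesis 1, on presentation: "Continuous variables will be considered as age-adjusted and sex-adjusted means with their standard deviations (SDs".
- Study Hypothesis 1, on the EAT analysis: "ANOVA model with adjustment for baseline will be used to calculate the changes". No age or sex term is named in that sentence.
- Study Hypothesis 2, on the LVM analysis: "ANOVA test with 95% CI will be used to calculate the changes". The sentence goes on to cover study parameters in general, at baseline, 3 and 6 months in both arms. It names no covariate.

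Study Timetable and Visit Procedures have LVM measured by echocardiography at baseline, 3 and 6 months, so baseline LVM will be in the database. The section on LVM and LVH measurement does speak of adjusting LVM, but that means indexing to body surface area or height. It is not covariate adjustment of the arm comparison.

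**The concern.** The plan adjusts the primary endpoint for its baseline but does not say that it does so for the secondary endpoint, which is measured at the same visits. The multivariable models later in Study Hypothesis 2 do not fill this gap. They select covariates by a univariate p-value to find determinants of the LVM change, and they do not estimate the F versus M difference.

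Without its baseline, the LVM comparison has a larger standard error than the collected data allow, and it carries any chance difference in baseline LVM between the arms. The Randomization section describes a restricted sequence and mentions no stratification that would limit such a difference.

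A second, smaller matter is that the age- and sex-adjusted means are tied to no model. A table could show one arm difference while the p-value beside it comes from a model that estimates a slightly different number. An SD beside an adjusted mean describes spread between patients, not the precision of that mean.

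**Working it through.** **Inputs from the documents.** Arm size: "Individuals will be randomized in two groups of 50 patients". Test level: "Two-tailed $p < 0.05$ indicates statistical significance". EAT effect: "A reduction of 15%, an absolute difference of 1.2 mm from baseline". EAT SDs: "Baseline SD of 3 is expected to lower to approximately 2 for the expected change".

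**Inputs the documents do not give.** There is no LVM SD, no LVM baseline–follow-up correlation ρ, and no R² for age and sex. I assume ρ from 0.5 to 0.9 with equal variance σ² at both visits, and a partial R² for age and sex from 0.02 to 0.10.

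**The plan's own figure.** Power is stated only for EAT: the sample will "provide the statistical power (80%) to detect an expected difference of -15% in the EAT before and after treatment with Dapagliflozin". As a within-arm before–after test with SD 3:
- 1.2 mm: Φ(1.2/(3/√50) − 1.96) = Φ(2.83 − 1.96) = 80.7%.
- 2 mm: Φ(4.71 − 1.96) = 99.7%.

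Both stated figures reproduce. A between-arm test of 1.2 mm gives 51.6% with SD 3 (SE 3√(2/50) = 0.6) and 85.1% with SD 2 (SE 2√(2/50) = 0.4). That mismatch is a separate issue; the SE of 0.4 is used below. There is no LVM power figure to reproduce.

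**LVM precision.** The per-patient variance is 2σ²(1−ρ) for an unadjusted change score and σ²(1−ρ²) for ANCOVA on baseline. The ratio is (1+ρ)/2. The last column starts from a notional 80% and uses Φ(2.80/√ratio − 1.96).

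| ρ (assumed) | Variance ratio | SE reduction | Equivalent extra patients (1/ratio − 1) | 80% power becomes |
|---|---|---|---|---|
| 0.5 | 0.75 | 13.4% | 33% | 90% |
| 0.7 | 0.85 | 7.8% | 18% | 86% |
| 0.8 | 0.90 | 5.1% | 11% | 84% |
| 0.9 | 0.95 | 2.5% | 5% | 82% |

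Estimating one covariate with 100 patients inflates the variance by about 1 + 1/(100−1−3) = 1.010. The ratios become roughly 0.76 to 0.96, so the gain remains across the range.

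**Chance imbalance.** The difference in baseline means has standard error σ√(2/50) = 0.2σ. An imbalance of that size shifts the unadjusted change contrast by (1−ρ) × 0.2σ, which is 0.10σ at ρ = 0.5 and 0.02σ at ρ = 0.9. This is the same gain seen another way and should not be counted twice: the variance difference, 0.04σ²[2(1−ρ) − (1−ρ²)], equals [(1−ρ) × 0.2σ]².

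**The only correlation the plan's figures suggest.** If the EAT SD of 2 is the SD of change and both visits have SD 3, then 2 × 3²(1−ρ) = 2², so ρ = 1 − 4/18 = 0.78. The ratio would be 0.89 and the SE reduction about 6%. This concerns EAT and is not evidence about LVM.

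**Displayed against tested EAT difference.** I compared a baseline-only model with one that adds age and sex in 4,000 simulated trials (SD 2, true effect −1.2 mm, age and sex R² 0.10).
- Mean estimates were −1.199 and −1.197 mm, so the target is the same.
- Within a single trial the two estimates differed with an SD of 0.14 mm, about 12% of 1.2 mm (0.14/1.2).
- Mean SEs were 0.400 and 0.384.
- By formula the SD of the gap is 0.4√R², or 0.06 to 0.13 mm for R² 0.02 to 0.10.

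**The case against.** The strongest reply is that the text is loose rather than wrong, and much of it stands. A reader might infer more than the documents support, in five ways.

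- *That the EAT test excludes age and sex, or that LVM is deliberately left unadjusted.* Both rest on silence. The age and sex sentence sits inside the Hypothesis 1 analysis paragraph and may be meant to cover the test. The safe statement is that no such covariate is named.
- *That reported and tested effects are different quantities.* In a randomised comparison with linear models both covariate sets estimate the same effect. They differ only by chance within one data set.
- *That leaving age and sex out of the EAT model wastes precision.* No R² is given. After the cost of estimating two covariates, power moves from 85.1% to between 85.1% and 87.9% for R² 0.02 to 0.10, and falls to 84.3% if R² is zero. Either choice is defensible if it is stated.
- *That the primary endpoint has no confidence interval.* The sentence promising a 95% CI refers to study parameters, which may include EAT.
- *That showing SDs misstates uncertainty sevenfold.* √50 = 7.07 is simply the ratio of SD to SE in any arm of 50. A labelled SD is a valid description of spread.

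It is also fair to say that LVM is a secondary endpoint with no power claim, and that the gain is small if ρ is high. What remains is that nothing in the documents supplies baseline LVM in the arm comparison.

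**Conclusion.** The point holds in a limited form. The LVM comparison names no baseline adjustment, while the parallel EAT analysis does. Adding it multiplies the variance of the LVM arm difference by 0.75 to 0.95, an SE reduction of 13% down to 2.5%. This rests on an assumed ρ of 0.5 to 0.9, equal variances at both visits, and an unadjusted change-score analysis as the comparator. The documents cannot narrow that range for LVM.

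The unlinked age- and sex-adjusted means are a matter of clarity. They leave room for a displayed difference that departs from the tested one by roughly 0.06 to 0.14 mm for EAT under the assumed R², without changing what is estimated. Neither part biases the randomised comparison. It is a free improvement.

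**What to change.** In Study Hypothesis 2, specify an ANCOVA for LVM with arm and baseline LVM as terms, the baseline being in the same form (unindexed or indexed) as the outcome. Use the parallel model for EAT in Study Hypothesis 1. State once, for each endpoint, whether age and sex are in the model. Take the displayed adjusted means and the test from that same model. Report the adjusted F-M difference with its 95% CI and p-value at each analysed visit, naming the visit. Keep raw mean ± SD for description only.

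The cost is wording in the Statistical Considerations. Baseline EAT and LVM are already scheduled, and the plan already presupposes age and sex for its adjusted means. No extra patients, visits or measurements are needed. The wording should be settled before any comparison by arm is run.
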